8.2.1 Hematologic Toxicities

- Radiation therapy will be held for grade 4 hematologic toxicity until grade <2 .(see table above) except lymphopenia.

8.2.2 Non-hematologic Toxicities

Neurotoxicity:

Based on treating oncologists' opinion.

8.3.1 Hematologic Toxicity

8.5 Dosing for Obese Patients will follow published ASCO guidelines

9.0 Ancillary Treatment/Supportive Care

9.1 Patients should receive full supportive care while on this study. This includes blood product support, antibiotic treatment, and treatment of other newly diagnosed or concurrent medical conditions. All blood products and concomitant medications such as anti-diarrheals, analgesics, and/or anti-emetics received from the first day of study treatment administration until 30 days after the final dose will be recorded in the medical records.

Chemotherapy interruptions will be determined by the Medical Oncology treating physician and will be assessed per standard clinical procedures for the particular chemotherapy being administered (as outlined in 8.2-8.5)

9.2 Skin changes are common complications of radiation therapy. Usual care will be provided. For dry skin, aloe vera based product or aquaphor can be prescribed. If the skin becomes erythematous and/or there is pruritis, topical steroid cream or topical Benadryl can be prescribed. Patients experiencing pain will be prescribed pain medication.

9.3 Antiemetics may be used at the discretion of the attending physician.

9.4 Other toxicities should be treated per standard of care: thrush/candida should be treated with antifungals (preferably nystatin as the first choice). Esophagitis should be treated with pain medications. Pneumonitis would be treated as clinically indicated (cough with anti-tussives (tessalon, dextromethorphan,) shortness of breath (with inhalers and bronchodilators), poor oxygen saturation (with O2). Patients should be hospitalized when clinically warranted.

9.5 Patients will receive ancillary treatment and supportive care that would otherwise be considered standard of care in the setting of chemotherapy, radiation, and surgery.

9.6 Radiation treatment will be interrupted at the discretion of the treating physician, as per standard of care. Generally, this would be for grade 4 in-field-toxicity (esophagus, pulmonary, skin) and/or grade 4 neutropenia with fever. (see 8.1 for specific recommendations)

10.0 Adverse Event (AE) Reporting and Monitoring

10.1 Definitions

Adverse Event- An untoward or undesirable experience associated with the use of a medical product (i.e. drug, device, biologic) in a patient or research subject.

Serious Adverse Event - Adverse events are classified as serious or non-serious. Serious problems/events can be well defined and include;

- death
- life threatening adverse experience
- hospitalization
- inpatient, new, or prolonged; disability/incapacity
- persistent or significant birth defect/anomaly

and/or per protocol may be problems/events that in the opinion of the sponsor-investigator may have adversely affected the rights, safety, or welfare of the subjects or others, or substantially compromised the research data.

All adverse events that do not meet any of the criteria for serious, should be regarded as **non-serious adverse events**.

Unanticipated Problems Involving Risks to Subjects or Others (UPIRTSO)- Any unanticipated problem or adverse event that meets the following three criteria:

- Serious: Serious problems or events that results in significant harm, (which may be physical, psychological, financial, social, economic, or legal) or increased risk for the subject or others (including individuals who are not research subjects). These include: (1) death; (2) life threatening adverse experience; (3) hospitalization - inpatient, new, or prolonged; (4) disability/incapacity - persistent or significant; (5) birth defect/anomaly; (6) breach of confidentiality and (7) other problems, events, or new information (i.e. publications, DSMB reports, interim findings, product labeling change) that in the opinion of the local investigator may adversely affect the rights, safety, or welfare of the subjects or others, or substantially compromise the research data, **AND**
- Unanticipated: (i.e. unexpected) problems or events are those that are not already described as potential risks in the protocol, consent document, not listed in the Investigator's Brochure, or not part of an underlying disease. A problem or event is "unanticipated" when it was unforeseeable at the time of its occurrence. A problem or event is "unanticipated" when it occurs at an increased frequency or at an increased severity than expected, **AND**
- Related: A problem or event is "related" if it is possibly related to the research procedures.

Preexisting Condition- A preexisting condition is one that is present at the start of the study. A preexisting condition should be recorded as an adverse event if the frequency, intensity, or the character of the condition worsens during the study period. At screening, any clinically significant abnormality should be recorded as a preexisting condition. At the end of the study, any new clinically significant findings/abnormalities that meet the definition of an adverse event must also be recorded and documented as an adverse event.

10.2 Recording Adverse Events

CTCAE term (AE description) and grade: The descriptions and grading scales found in the revised NCI Common Terminology Criteria for Adverse Events (CTCAE) version 4.0 will be utilized for AE reporting. All appropriate treatment areas should have access to a copy of the CTCAE version 4.0. A copy of the CTCAE version 4.0 can be downloaded from the CTEP web site:

10.21 Adverse event monitoring and reporting are a routine part of every clinical trial. First, identify and grade the severity of the event using the CTCAE version 4.0. Next, determine whether the event is expected or unexpected and if the adverse event is related to the medical treatment or procedure. With this information, determine whether the event must be reported as an expedited report (see Section 10.3).

10.22 Assessment of Attribution

When assessing whether an adverse event is related to a medical treatment or procedure, the following attribution categories are utilized:

Definite - The adverse event is clearly related to the agent(s).

Probable - The adverse event is likely related to the agent(s).

Possible - The adverse event may be related to the agent(s).

Unlikely - The adverse event is doubtfully related to the agent(s).
Unrelated - The adverse event is clearly NOT related to the agent(s).

Events determined to be possibly, probably or definitely attributed to a medical treatment suggest there is evidence to indicate a causal relationship between the drug and the adverse event.

10.3 Reporting of Serious Adverse Events and Unanticipated Problems

When an adverse event has been identified, the study team will take appropriated action necessary to protect the study participant and then complete the Study Adverse Event Worksheet and log. The sponsor-investigator will evaluate the event and determine the necessary follow-up and reporting required.

- a. Serious Adverse Events will be reported as part of regular adverse event reporting mechanisms via the data capture system and logged for review reporting.
- b. General reporting instructions
The Mayo IND and/or MCCC Compliance will assist the sponsor-investigator in the processing of expedited adverse events and forwarding of suspected unexpected serious adverse reactions (SUSARs) to the FDA and IRB.
Use Mayo Expedited Event Report form

[REDACTED] or investigational agents or commercial/investigational agents on the same arm.

10.31 Investigator Reporting: Notifying the Mayo IRB:

The IRB requirements reflect the guidance documents released by the Office of Human Research Protections (OHRP), and the Food and Drug Administration (FDA) in early 2007 and are respectively entitled “Guidance on Reviewing and Reporting Unanticipated Problems Involving Risks to Subjects or Others and Adverse Events” and “Guidance for Clinical Investigators, Sponsors, and IRBs: Adverse Event Reporting – Improving Human Subject Protection.”

- 10.311 According to Mayo IRB Policy any serious adverse event (SAE) which the Principal Investigator has determined to be a UPIRTSO must be reported to the Mayo IRB as soon as possible but no later than 5 working days after the investigator first learns of the problem/event.
- 10.312 NonUPIRTSO – the investigator reports problems or events that do NOT meet criteria of an UPIRTSO in summary format at the time of the next continuing review. The investigator monitors the severity and frequency of subsequent nonUPIRTSOs.

Consider the following information to collect when developing any forms for documentation of adverse events.

Example

Information collected on the adverse event worksheet (and entered in the research database):

- Subject's name:
- Medical record number:
- Disease/histology (if applicable):
- The date the adverse event occurred:
- Description of the adverse event:
- Relationship of the adverse event to the research (drug, procedure, or intervention):
- If the adverse event was expected:
- The severity of the adverse event: (use a table to define severity scale 1-5)
- If any intervention was necessary:
- Resolution: (was the incident resolved spontaneously, or after discontinuing treatment)
- Date of Resolution:

The investigator will review all adverse event reports to determine if specific reports need to be made to the IRB and FDA. The investigator will sign and date the adverse event report when it is reviewed. For this protocol, only directly related SAEs/UPIRTSOs will be reported to the IRB.

10.4 Adverse events to be graded at each evaluation and pretreatment symptoms/conditions to be evaluated at baseline per the CTCAE v4.0 grading unless otherwise stated in the table below:

System Organ Class (SOC)	Adverse event/Symptoms	Baseline	Each evaluation
Skin and subcutaneous disorders	Radiation dermatitis	X	X
Resp, thoracic & med disorders	Pneumonitis	X	x
GI disorders	Esophagitis	X	x
Blood & lymphatic	Febrile neutropenia	X	x

10.41 Submit via appropriate *reporting mechanisms* (i.e., paper or electronic) the following AEs experienced by a patient and not specified in Section 10.4:

10.4.11 Grade 2 AEs deemed possibly, probably, or definitely related to the radiation.

10.4.12 Grade 3 and 4 AEs regardless of attribution to the study treatment or procedure.

10.4.13 Grade 5 AEs (Death)

10.4.131 Any death within 30 days of the patient's last study treatment or procedure regardless of attribution to the study treatment or procedure

10.4.132 Any death more than 30 days after the patients last study treatment or procedure that is felt to be at least possibly treatment related must also be

submitted as a Grade 5 AE, with a CTCAE type and attribution assigned.

10.5 Monitoring and Auditing

The investigator will permit study-related monitoring, audits, and inspections by the IRB, and government regulatory agencies, of all study related documents (e.g. source documents, regulatory documents, data collection instruments, study data etc.). The investigator will ensure the capability for inspections of applicable study-related facilities (e.g. pharmacy, diagnostic laboratory, etc.).

Participation as an investigator in this study implies acceptance of potential inspection by government regulatory authorities and applicable compliance offices

10.51 Medical Monitoring

It is the responsibility of the Principal Investigator to oversee the safety of the study at his/her site. This safety monitoring will include careful assessment and appropriate reporting of adverse events as noted above, as well as the construction and implementation of a site data and safety-monitoring plan (see section 10.5 “Monitoring and Auditing”). Medical monitoring will include a regular assessment of the number and type of serious adverse events. “Any serious adverse events will be followed up by the sentinel event reporting procedure”

11.0 Treatment Evaluation

NOTE: This study uses protocol RECIST v1.1 template dated 2/16/2011. See the footnote for the table regarding measurable disease in Section 11.44, as it pertains to data collection and analysis.

Response and progression will be evaluated in this study using the new international criteria proposed by the revised Response Evaluation Criteria in Solid Tumors (RECIST) guidelines (version 1.1)¹³ Changes in the largest diameter (unidimensional measurement) of the tumor lesions and the short axis measurements in the case of lymph nodes are used in the RECIST guideline.

11.1 Schedule of Evaluations: For the purposes of this study, patients should be reevaluated every 12-16 weeks during the active phase.

11.2 Definitions of Measurable and Non-Measurable Disease

11.21 Measurable Disease

11.211 A non-nodal lesion is considered measurable if its longest diameter can be accurately measured as ≥ 2.0 cm with chest x-ray, or as ≥ 1.0 cm with CT scan, CT component of a PET/CT, or MRI.

11.212 A superficial non-nodal lesion is measurable if its longest diameter is ≥ 1.0 cm in diameter as assessed using calipers (e.g. skin nodules) or imaging. In the case of skin lesions, documentation by color photography, including a ruler to estimate the size of the lesion, is recommended.

11.213 A malignant lymph node is considered measurable if its short axis is ≥ 1.5 cm when assessed by CT scan (CT scan slice thickness recommended to be no greater than 5 mm).

Tumor lesions in a previously irradiated area are considered measurable disease under the following conditions: to determine local-regional control.

11.22 Non-Measurable Disease

11.221 All other lesions (or sites of disease) are considered non-measurable disease, including pathological nodes (those with a short axis ≥ 1.0 to < 1.5 cm). Bone lesions, leptomeningeal disease, ascites, pleural/pericardial effusions, lymphangitis cutis/pulmonis, inflammatory breast disease, and abdominal masses (not followed by CT or MRI), are considered as non-measurable as well.

Note: ‘Cystic lesions’ thought to represent cystic metastases can be considered as measurable lesions, if they meet the definition of measurability described above. However, if non-cystic lesions are present in the same patient, these are preferred for selection as target lesions. In addition, lymph nodes that have a short axis < 1.0 cm are considered non-pathological (i.e., normal) and should not be recorded or followed.

11.3 Guidelines for Evaluation of Measurable Disease

11.31 Measurement Methods:

- All measurements should be recorded in metric notation (i.e., decimal fractions of centimeters) using a ruler or calipers.
- The same method of assessment and the same technique must be used to characterize each identified and reported lesion at baseline and during follow-up. For patients having only lesions measuring at least 1 cm to less than 2 cm must use CT imaging for both pre- and post-treatment tumor assessments.
- Imaging-based evaluation is preferred to evaluation by clinical examination when both methods have been used at the same evaluation to assess the antitumor effect of a treatment.

11.32 Acceptable Modalities for Measurable Disease:

- Conventional CT and MRI: This guideline has defined measurability of lesions on CT scan based on the assumption that CT slice thickness is 5 mm or less. If CT scans have slice thickness greater than 5 mm, the minimum size for a measurable lesion should be twice the slice thickness.
- As with CT, if an MRI is performed, the technical specifications of the scanning sequences used should be optimized for the evaluation of the type and site of disease. The lesions should be measured on the same pulse sequence. Ideally, the same type of scanner should be used and the image acquisition protocol should be followed as closely as possible to prior scans.

Body scans should be performed with breath-hold scanning techniques, if possible.

- PET-CT: If the site can document that the CT performed as part of a PET-CT is of identical diagnostic quality to a diagnostic CT (with IV and oral contrast), then the CT portion of the PET-CT can be used for RECIST measurements and can be used interchangeably with conventional CT in accurately measuring cancer lesions over time.
- Physical Examination: For superficial non-nodal lesions, physical examination is acceptable, but imaging is preferable, if both can be done. In the case of skin lesions, documentation by color photography, including a ruler to estimate the size of the lesion, is recommended.
- FDG-PET: FDG-PET scanning is allowed to complement CT scanning in assessment of progressive disease [PD] and particularly possible 'new' disease. A 'positive' FDG-PET scanned lesion is defined as one which is FDG avid with an uptake greater than twice that of the surrounding tissue on the attenuation corrected image; otherwise, an FDG-PET scanned lesion is considered 'negative.' New lesions on the basis of FDG-PET imaging can be identified according to the following algorithm:
 - a. Negative FDG-PET at baseline with a positive FDG-PET at follow-up is a sign of PD based on a new lesion.

11.33 Measurement at Follow-up Evaluation:

- In the case of stable disease (SD), follow-up measurements must have met the SD criteria at least once after study entry at a minimum interval of 12-16 weeks (see Section 11.44).
- The cytological confirmation of the neoplastic origin of any effusion that appears or worsens during treatment when the measurable tumor has met criteria for response or stable disease is mandatory to differentiate between response or stable disease (an effusion may be a side effect of the treatment) and progressive disease.
- Cytologic and histologic techniques can be used to differentiate between PR and CR in rare cases (e.g., residual lesions in tumor types such as germ cell tumors, where known residual benign tumors can remain.)

11.4 Measurement of Effect

11.41 Target Lesions & Target Lymph Nodes

- Measurable lesions (as defined in Section 11.21) up to a maximum of 5 lesions representative of all involved organs, should be identified as "Target Lesions" and recorded and measured at baseline. These lesions can be non-

nodal or nodal (as defined in 11.21), where no more than 2 lesions are from the same organ and no more than 2 malignant nodal lesions are selected.

Note: If fewer than 5 target lesions and target lymph nodes are identified (as there often will be), there is no reason to perform additional studies beyond those specified in the protocol to discover new lesions.

- Target lesions and target lymph nodes should be selected on the basis of their size, be representative of all involved sites of disease, but in addition should be those that lend themselves to reproducible repeated measurements. It may be the case that, on occasion, the largest lesion (or malignant lymph node) does not lend itself to reproducible measurements in which circumstance the next largest lesion (or malignant lymph node), which can be measured reproducibly should be selected.
- Baseline Sum of Dimensions (BSD): A sum of the longest diameter for all target lesions plus the sum of the short axis of all the target lymph nodes will be calculated and reported as the baseline sum of dimensions (BSD). The BSD will be used as reference to further characterize any objective tumor response in the measurable dimension of the disease.
- Post-Baseline Sum of the Dimensions (PBSD): A sum of the longest diameter for all target lesions plus the sum of the short axis of all the target lymph nodes will be calculated and reported as the post-baseline sum of dimensions (PBSD). If the radiologist is able to provide an actual measure for the target lesion (or target lymph node), that should be recorded, even if it is below 0.5 cm. If the target lesion (or target lymph node) is believed to be present and is faintly seen but too small to measure, a default value of 0.5 cm should be assigned. If it is the opinion of the radiologist that the target lesion or target lymph node has likely disappeared, the measurement should be recorded as 0 cm.
- The minimum sum of the dimensions (MSD) is the minimum of the BSD and the PBSD.

11.42 Non-Target Lesions & Non-Target Lymph Nodes

Non-measurable sites of disease (Section 11.22) are classified as non- target lesions or non-target lymph nodes and should also be recorded at baseline. These lesions and lymph nodes should be followed in accord with 11.433.

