11.43 Response Criteria

11.431 All target lesions and target lymph nodes followed by CT/MRI/PET-CT/ /physical examination must be measured on re-evaluation at evaluation times specified in Section 11.1. Specifically, a change in objective status to either a PR or CR cannot be done without re-measuring target lesions and target lymph nodes.

Note: Non-target lesions and non-target lymph nodes should be evaluated at each assessment, especially in the case of first response or confirmation of response. In selected circumstances, certain non-target organs may be evaluated less frequently. For example, bone scans may need to be repeated only when complete response is identified in target disease or when progression in bone is suspected.

11.432 Evaluation of Target Lesions

- Complete Response (CR): All of the following must be true:
 - a. Disappearance of all target lesions.
 - b. Each target lymph node must have reduction in short axis to <1.0 cm.
- Partial Response (PR): At least a 30% decrease in PBSD (sum of the longest diameter for all target lesions plus the sum of the short axis of all the target lymph nodes at current evaluation) taking as reference the BSD (see Section 11.41).
- Progression (PD): At least one of the following must be true:
 - a. At least one new malignant lesion, which also includes any lymph node that was normal at baseline (< 1.0 cm short axis) and increased to ≥ 1.0 cm short axis during follow-up.
 - b. At least a 20% increase in PBSD (sum of the longest diameter for all target lesions plus the sum of the short axis of all the target lymph nodes at current evaluation) taking as reference the MSD (Section 11.41). In addition, the PBSD must also demonstrate an absolute increase of at least 0.5 cm from the MSD.
 - c. See Section 11.32 for details in regards to the requirements for PD via FDG-PET imaging.
- Stable Disease (SD): Neither sufficient shrinkage to qualify for PR, nor sufficient increase to qualify for PD taking as reference the MSD.

11.433 Evaluation of Non-Target Lesions & Non-target Lymph Nodes

- Complete Response (CR): All of the following must be true:
 - a. Disappearance of all non-target lesions.
 - b. Each non-target lymph node must have a reduction in short axis to <1.0 cm.

- Non-CR/Non-PD: Persistence of one or more non-target lesions or non-target lymph nodes.

- Progression (PD): At least one of the following must be true:

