 - a. At least one new malignant lesion, which also includes any lymph node that was normal at baseline (< 1.0 cm short axis) and increased to ≥ 1.0 cm short axis during follow-up.
 - b. Unequivocal progression of existing non-target lesions and non-target lymph nodes. (NOTE: Unequivocal progression should not normally trump target lesion and target lymph node status. It must be representative of overall disease status change.)
 - c. See Section 11.32 for details in regards to the requirements for PD via FDG-PET imaging.

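### Section 11.42 leaves measurable nodes and lesions beyond the target cap in neither lesion set, so their growth meets none of the written progression criteria apart from a narrow PET conversion rule

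*Combined protocol and SAP*

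**What the plan says.** Four parts of Section 11 decide where a lesion belongs.

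- **Measurable (11.21).** "A malignant lymph node is considered measurable if its short axis is ≥ 1.5 cm when assessed by CT scan". A non-nodal lesion is measurable from 1.0 cm on CT.
- **Non-measurable (11.22).** "All other lesions (or sites of disease) are considered non-measurable disease, including pathological nodes", with the node range given as 1.0 to <1.5 cm. This is the complement of 11.21.
- **Target (11.41).** Measurable lesions, "up to a maximum of 5 lesions representative of all involved organs", where "no more than 2 lesions are from the same organ and no more than 2 malignant nodal lesions are selected".
- **Non-target (11.42).** "Non-measurable sites of disease (Section 11.22) are classified as" non-target, and these are also to be recorded at baseline.

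Progression (11.432, 11.433) then rests on the target sum ("At least a 20% increase in PBSD (sum of the longest diameter for all target lesions" and target nodes, with an absolute rise of 0.5 cm), on new lesions or nodes below 1.0 cm at baseline that enlarge, on "Unequivocal progression of existing non-target lesions and non-target lymph nodes", or on the PET rule in 11.32. The 11.44 table combines target, non-target and new disease. Section 16.311 bases PFS on centrally reviewed progression.

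**The concern.** The two lesion sets do not cover all known disease. A measurable node or lesion that the cap keeps off the target list is still measurable, so it does not fall under 11.22, and 11.42 does not pick it up. The result is the reverse of what one would want: a third node of 1.2 cm is non-target and followed, while a third node of 2.0 cm is in no set.

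Such a node is known disease inside the treated volume, since 7.1.6 includes nodes above 1.0 cm in short diameter in the IGTV. Regional control of that disease is part of what a comparison of 60 and 72 Gy should detect. If growth there is not called progression, the patient stays progression-free until some other event occurs. The 1-year PFS rate that picks the winning arm is then too high in that patient's arm.

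**Working it through.** The plan states no figure on this point, so there is none to reproduce. The check applies each written rule to one case: a malignant node of at least 1.5 cm at baseline, left unselected because two nodes are already targets.

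**Does its growth meet a progression rule?**

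1. 11.432a and 11.433a (new lesion, or node normal at baseline): no. It was present and above 1.0 cm.
2. 11.432b (target sum): no. It is not in the sum.
3. 11.433b (existing non-target disease): no. It is not in the non-target set.
4. 11.32 (FDG-PET): only if it was PET-negative at baseline and later positive. That is conversion, not growth, and 7.1.6 describes involved disease as generally warmer than blood pool on PET, so the exception is narrow.
5. 11.44: reads only target, non-target and new disease, so it adds nothing.

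**Illustration (sizes assumed).** Target nodes are 2.4 and 2.0 cm, so the baseline sum is 2.4 + 2.0 = 4.4 cm. The third, unselected node grows from 1.8 to 3.6 cm.

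- *Targets respond.* They shrink to 0.9 and 0.8 cm; the sum is 1.7 cm and the change is (1.7 − 4.4)/4.4 = −61.4%. Both are below 1.0 cm, so target status is CR. As written, overall status is CR if any listed non-target disease has also cleared. If the third node were non-target, CR would be ruled out and the best status would be PR. Whether it is PD would be a reader's decision under 11.433b.
- *Targets unchanged.* The sum stays at 4.4 cm, a change of 0%, so the status is SD. If the third node were non-target, its doubling would be assessable under 11.433b. For scale only: a sum of all three nodes would go from 6.2 to 8.0 cm, which is 8.0/6.2 − 1 = +29.0% and +1.8 cm, beyond the 20% and 0.5 cm thresholds.

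**Weight of one patient.** With 21 per arm (16.21), treating 1-year PFS as a simple proportion, one patient is 1/21 = 4.8 points. A difference of three patients is 3/21 = 14.3 points, below the 15-point margin. A difference of four is 4/21 = 19.0 points, above it. One reclassified patient can therefore cross the line when the arms are that close.

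**How many patients?** Let p be the share of patients with a surplus measurable node or lesion, and q the share of those in whom it grows within the year with no other PFS event. The shift in an arm's 1-year PFS is p × q. The documents give neither. Assuming p = 10% to 40%, carriers number 21 × p = 2.1 to 8.4 per arm. Assuming also q = 10%, missed progressions number 0.21 to 0.84 per arm, or 1 to 4 points. Both inputs are assumptions and show only the order of size.

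**The case against.** The strongest reply is that Section 11.0 adopts RECIST v1.1 by name, the 11.44 footnote says the template was aligned with it, and the primary analysis uses central reads. Section 11.42 also does not say that *only* non-measurable sites are non-target. A reader might infer from the gap that growth of the surplus node is not progression under any rule. The documents do not support that: the guideline's text is not in them, and central readers may apply its own definition. What stands is that no sentence in the protocol classes this node, and that sites working from 11.42 and readers working from the guideline could reach different calls.

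A second reply is that the remedy would not settle every case. The note to 11.433b says that non-target progression should not ordinarily override target status and must reflect a change in overall disease. With responding targets, one growing node may still not be called PD. This is correct. The remedy makes the growth assessable; it does not make it automatic progression.

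Three further inferences are tempting and should not be drawn.

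- *That local-regional failure is also affected.* Section 16.324 defines it by site, as the original tumour and adenopathy (GTV), and 7.1.6 brings nodes of this size into the treated volume. The node is already covered. The mismatch is that growth could count as local-regional failure while the patient remains progression-free.
- *That a false CR biases an endpoint.* CR versus PR does not enter PFS, and response is not a stated objective. Response is mentioned in 16.25 only as one consideration in a decision to terminate the study.
- *That the case is common, and that all carriers are misclassified.* The documents give no frequency of three or more nodes of at least 1.5 cm, and carrying such a node is not the same as losing a PFS event.

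**Conclusion.** The point holds on the protocol's own wording. Measurable disease beyond the 11.41 limits is in neither lesion set, is not recorded at baseline under either heading, and can grow without meeting a written progression criterion, apart from PET conversion. Progression in the primary endpoint can be missed or delayed as a result. The effect on response status is real but touches no stated endpoint.

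The size cannot be computed from the documents. The firm figure is 4.8 points of 1-year PFS per affected patient at 21 per arm. It applies only when the surplus node grows within the year, nothing else counts as a PFS event by then, and the central read follows 11.42 as written. The gap should be closed because the correction is cheap and the endpoint is primary. It does not by itself put the comparison in doubt.

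**What to change.** Reword 11.42 along these lines: *All sites of disease not selected as target lesions or target lymph nodes, that is, non-measurable sites (Section 11.22) and measurable lesions or nodes beyond the 11.41 limits, are classified as non-target and recorded at baseline.*

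Sections 11.433 and 11.44 can stay as they are. Growth of a surplus node then becomes assessable under 11.433b, subject to its note, and persistence rules out CR. Give sites, through the CRF instruction, and the central review panel the same wording, so that both work from one rule.

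The cost is one sentence, the matching CRF instruction and a small extra recording effort. No new imaging is needed: the lesions are on scans already taken, and baseline CTs of patients already enrolled can be re-read.
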